1.3.3 Determination of the dropout rate

Based on the LOTS study, 57 out of 60 (95%) alglucosidase alfa treated patients remained in the study at Month 12 with evaluable FVC data and 54 out of 60 (90%) patients remained on the study at Month 18. A separate uncontrolled study (EMBASSY) with a similar patient population enrolled a total of 16 patients for planned 6 months follow-up. Among those, 1 patient (6.3%) had missing data at 6 months. To allow potential variability between trials and to retain a reasonable power for the per-protocol population analysis, a 10% dropout rate was assumed which corresponds to a total sample size of approximately 96 patients.

1.3.4 Power calculations with different effect size assumptions

The power calculations for additional assumptions of effect size are presented in [Table 4](#).

Table 4 - Power for non-inferiority test and superiority test under different effect size and standard deviations

Standard Deviation assumption (based on LOTS patients at Month 12)	Treatment difference	Power for NI test (NI margin = 1.1)	Power for superiority test
5.0 (estimated from the MMRM model with all patients data)			
	1.5	66.4%	27.9%
	2.0	81.1%	45.0%
	2.5	91.0%	63.0%
	3.0	96.4%	78.5%
	3.5	98.8%	89.4%
5.1 (estimated from within arm SD from evaluable alglucosidase alfa patients only)			
	1.5	64.7%	27.0%
	2.0	79.6%	43.5%
	2.5	89.9%	61.3%
	3.0	95.8%	76.9%
	3.5	98.5%	88.2%

[figure not shown]
1.4 STUDY PLAN

For each patient who signs the informed consent, the study consists of:

- Screening/baseline visit: occurs within 14 days prior to randomization,
- Blinded treatment period (PAP), except for the subgroup of patients aged 3 to < 18 years enrolling directly in the open-label long term follow-up phase: a 49-week blinded treatment phase, in which patients will receive an IV infusion of 20 mg/kg avalglucosidase alfa or alglucosidase alfa qow. This phase of the study will be referred as PAP in this document.
- Open-label avalglucosidase alfa long term treatment period: an up to 96-week open label avalglucosidase alfa long term follow-up. All patients will receive an IV infusion of 20 mg/kg avalglucosidase alfa qow for long-term follow-up.
- An extended open-label avalglucosidase alfa long term follow-up period will last up to 144 additional weeks (or up to avalglucosidase alfa approval in the country of the patient, whichever comes first) for all patients (additional open label avalglucosidase alfa long term follow up Phase).
- Both open-label period and extended open-label period will be referred to as the Extension Treatment Period (ETP) in this document.
- An up to 4 week post treatment observation period.

Study flowchart is described in Figure 1 below. The schedule of efficacy assessments is described in Section 7.

Figure 1 – General 2Study Design

1.5 MODIFICATIONS TO THE STATISTICAL SECTION OF THE PROTOCOL

The current SAP is based on protocol amendment 3 (dated 10 Apr 2019). This section summarizes major changes to the protocol statistical section with emphasis on changes after study start (after the first patient was enrolled). The protocol history table below gives the timing, rationale and key details of major changes to the protocol statistical section.

Protocol amendment statistical changes

Amendment Number	Date Approved	Description of Statistical Changes	Brief Rationale
3	10-Apr-2019	Updated definition of Safety Population to include up to 2 pediatric patients who will be enrolled directly in the open-label avalglucosidase alfa long term follow-up phase	In order to comply with Health Authority requirements to enroll a certain number of pediatric patients, up to 2 additional pediatric patients will be enrolled directly in the open-label avalglucosidase alfa long-term follow-up phase where they will receive avalglucosidase alfa
3	10-Apr-2019	Added following superiority test to the hierarchical testing ‘% predicted change from baseline to Week 49 for MEP’.	We will have chance to make claim in the label for the secondary endpoint MEP
3	10-Apr-2019	Removed non-inferiority test of 6MWT in the fixed sequence testing to control multiplicity.	Updated in accordance with the feedback received from Regulatory Agency.

1.6 STATISTICAL MODIFICATIONS MADE IN THE STATISTICAL ANALYSIS PLAN

The following main modifications have been made in this version of SAP

- Placebo-based imputation is removed since they may bias towards equivalence and thus is not conservative for NI trial.
- Added potential sensitivity analyses with respect to the constancy assumption based on covariate-adjustment fixed margin approach and/or covariate-adjustment synthesis method as proposed by Nie and Soon (2) based on feedback from health authority.
- Added the concept of estimand based on feedback from health authority.
- Additional results on Type I error rates and power were added in Section 2.5.1 in response to FDA question/request for information item no.1 dated 02 September 2016.
- The SAP is revised to cover statistical analyses in both PAP and ETP.

- In response to FDA question/request for information item no.2 dated 02 September 2016:
 - Background data on determination of dropout rate were added in Section 1.3.3
 - Section 2.5 was revised to add the sentence that “If the pure ITT (all randomized patients) population is different from the mITT population, we plan to perform a sensitivity analysis in this population as well to assess the robustness of the results.”
- The Appendix on Potentially Clinically Significant Abnormalities Criteria was updated to correct a typo on children diastolic blood pressure criteria, i.e., increase/decrease from baseline should be ≥ 10 mmHg instead of ≥ 20 mmHg.
- In response to FDA question/request for information dated 19 July 2019:
 - Added Global Lung Initiative (GLI) 2012 reference equations to calculate FVC % predicted values
 - Added new threshold of 27.5 meters to define the 6MWT responder in addition to the current 3 thresholds.
- In response to FDA question/request for information dated 14 January 2020:
 - Proposed the treatment policy estimand to assess the treatment effect regardless of occurrence of intercurrent events. All collected efficacy data will be used in analysis to be aligned to the treatment policy estimand.
- In response to meeting discussion with FDA on 20 February 2020,
 - Added a within patient comparison in FVC (% predicted) between Week 49 and Week 97 for patients who were initially randomized to Alglucosidase alfa in PAP and then crossed over to Avalglucosidase alfa in ETP
 - Updated immunogenicity analysis. Some revisions of immunogenicity analysis are made to be consistent with integrated immunogenicity analysis plan.
- In response to FDA advice/request for information dated 13 April 2020:
 - Added an analysis of covariance (including baseline FVC, age, gender, treatment group as covariates) for the endpoint of change from baseline in FVC (% predicted) at Week 49 or the last visit prior to initiation of an alternative treatment prior to Week 49. For those patients who prematurely discontinued prior to Week 49 but with unknown alternative treatment information, their last value prior to dropout will be used in the analysis.
 - Added analysis to assess the within-subject changes from baseline in PD marker with respect to the changes in the status and/or titer value of ADA/NAb (neutralizing antibodies).

2 STATISTICAL AND ANALYTICAL PROCEDURES

The PAP analysis will be performed after all patients have completed the 12-month (49 week) blinded treatment phase and will include a formal database lock and unblinding of the study treatment arms, and analyses of efficacy, safety, pharmacodynamic, and pharmacokinetic data. A CSR will be prepared after the PAP analysis.

After the primary analysis for PAP is completed, interim analyses may be performed during the open-label extension period to provide additional information for regulatory purpose. those additional analyses after PAP will be considered supportive purpose.

The final ETP analyses will be performed after all patients completed ETP. A final database lock will occur, and a final CSR will be prepared after the ETP analyses.

2.1 ANALYSIS ENDPOINTS

2.1.1 Demographic and baseline characteristics

The baseline value is defined as the last non-missing value prior to first treatment, unless otherwise specified. In ETP analyses, when needed, the ETP baseline value is defined as the last non-missing value prior to first infusion in ETP.

Demographic characteristics

Demographic variables are gender (Male, Female), race (American Indian or Alaska Native, Asian, Black or African American, Native Hawaiian or other Pacific Island, White, Not reported), regions, weight, height, BMI, head circumference, age at study entry (informed consent), and randomization strata.

Medical/Surgical history

Medical (or surgical) history includes prior or existing condition in different body systems as well as prior or existing medical conditions/surgical procedures of specific interest.

Disease characteristics at baseline

Pompe disease history includes age at Pompe disease diagnosis, age at first symptoms of Pompe disease, and time from these events to 1st infusion of study drug.

Pompe medical history includes,

- Cardiovascular history (congestive heart failure, current NYHA (the New York Heart Association) heart failure classification, evidence of cardiac involvement),
- Ear, nose, throat medical history (enlarged tongue, hearing loss, hepatomegaly, gastroesophageal reflux),
- Respiratory history (tracheostomy history, pneumonia, sleep disturbances, sleep apnea, use of non-invasive respiratory support),

- Musculoskeletal history (muscle weakness, scoliosis, joint contractures, and current ambulatory status, assisted walking device and wheelchair use).
- Family history of Pompe disease history includes confirmed Pompe disease in other family members.

Vital signs

Vital signs at baseline are heart rate, systolic and diastolic blood pressure, respiratory rate, temperature, and oxygen saturation. The baseline values for vital signs are the last non-missing assessment prior to the first study treatment by comparing the infusion time and measurement time.

Electrocardiogram variables

The baseline ECG is defined as the average of triplicate values at the baseline visit and prior to the first infusion of the study drug.

Immunogenicity status

The immunogenicity evaluation at baseline includes antibody status (positive or negative) and magnitude (titer) of the anti-drug antibodies (ADA).

2.1.2 Prior or concomitant medications

Medications and therapies taken by the patient during the 30-day period prior to the Screening/Baseline evaluation visit and during the course of the study will be recorded in the electronic Case Report Forms (e-CRF).

All medications will be coded using the World Health Organization-Drug Dictionary (WHO-DD) using the version in effect at Sanofi at the time of database lock.

- Prior medications are those the patient used prior to first investigational medicinal product (IMP) intake. Prior medications can be discontinued before first administration or can be ongoing during treatment phase.
- Concomitant medications are any treatments received by the patient concomitantly to the IMP, from 1st study treatment to the end of treatment + 30 days. A given medication can be classified both as a prior medication and as a concomitant medication. Concomitant medications do not include medications started during the post-treatment period (as defined in the observation period in [Section 2.1.4](#)).
- Post-treatment medications are those the patient took in the period running from the 30 days after last IMP intake up to the end of the study.

The use (if any) of mechanical ventilation (including both invasive and noninvasive), as well as assistive device use will be recorded on the e-CRF.

Any technical details related to computation, dates, imputation for missing dates are described in [Section 2.10](#).

2.1.3 Efficacy endpoints

The baseline value for efficacy endpoints is the last non-missing assessment prior to study treatment and no later than the randomization date. The ETP baseline value for efficacy endpoints is the last non-missing assessment prior to the first study treatment in ETP.

2.1.3.1 Primary efficacy endpoint

The primary efficacy endpoint is the change from baseline to Week 49 in FVC (% predicted) in the upright position. FVC will be reported in absolute value in liters, as well as the percent of predicted normal values based on Global Lung Initiative (GLI) 2012 reference equations (3). The FVC percent of predicted values will be calculated based on FVC in liters, gender, race (classified as Caucasian, Asian and African-American, and Other/Mixed), age (at least one decimal place in years), and height (in cm) at the time of each assessment and will be reported centrally from Biomedical Systems (BMS), following pulmonary software specification and user requirement (4).

The FVC percent predicted value is calculated as:

$(\text{actual FVC measurement}/\text{predicted value of FVC}) * 100.$

The GLI-2012 regression equations and lookup tables are used to calculate predicted values of FVC (1). FVC is predicted according to the following equation in the EFC14028 trial:

$M = \exp(a_0 + a_1 \cdot \ln(\text{Height}) + a_2 \cdot \ln(\text{Age}) + a_3 \cdot \text{black} + a_4 \cdot \text{NEAsia} + a_5 \cdot \text{SEAsia} + a_6 \cdot \text{Other} + \text{Mspline})$

where

Black = 1 if a subject is African American, otherwise = 0

NorthEastAsia = 1 if a subject is from North East Asia, otherwise = 0

SouthEastAsia = 1 if a subject is from South East Asia, otherwise = 0

Other = 1 if subject is 'other ethnic group' or mixed ethnicity, otherwise = 0

Coefficients a(n) depend on sex and are given by lookup table

Mspline is age-varying coefficients, given by lookup table for each type of sex

For the analysis purpose, the age will be calculated based on $(\text{assessment date} - \text{birth date} + 1)/365.25$. Height will be based on the most recent valid value at or prior to the assessment date.

Since baseline FVC (% predicted) is used for randomization stratification purposes, no patient should have a missing baseline value. The schedule of assessments is provided in [Section 7](#).

2.1.3.2 Secondary efficacy endpoint(s)

The key secondary efficacy endpoint for the study is the total distance (meters) walked during six-minute walk test (6MWT). The additional secondary efficacy endpoints are:

- Pulmonary function testing: maximum expiratory pressure (MEP) and percent predicted, maximum inspiratory pressure (MIP) and percent predicted,
- Hand-held dynamometry (lower extremity strength): lower extremity summary score and individual muscle group and percent predicted from the muscle groups of Hip Flexion, Hip Extension, Hip Abduction, Hip Adduction, Knee Flexion, Knee Extension, Ankle Dorsiflexion, Ankle Plantar Flexion,
- Quick motor function test: total score of the QMFT,
- 12-item short-form health survey: the physical component summary (PCS) and mental component summary (MCS) scales from the survey.

The planned schedule of assessments for secondary efficacy endpoints is provided in [Section 7](#).

Six-minute walk test

The 6MWT (5) will be performed to assess functional capacity in the late-onset Pompe disease population. The primary outcome measure of the 6MWT is the distance walked in 6 minutes recorded in meters. Test equipment and administration techniques will be standardized among the investigational sites. The percent predicted value will be calculated based on the normal reference equations from (6) and (7), which cover the age range in this study. A similar approach was used by Montes et al (8). For analysis purposes, the age at each assessment will be calculated based on (assessment date - birth date + 1)/365.25. Height (which is to be assessed annually for patients with age ≥ 18 years and every 3 months for patients with age < 18 years) will be based on the most recent valid value at or prior to the assessment date.

Table 5 - Equations for calculating reference value for % predicted total distance walked in 6MWT

Reference	Age at baseline	Gender	Equation
(6)	≥ 18 years	Male and Female	$868.8 - 2.99 * \text{age} - 74.7 * \text{sex}$
(7)	< 18 years	Male	$196.72 + 39.81 * \text{age} - 1.36 * \text{age}^2 + 132.28 * \text{height}$
	< 18 years	Female	$188.61 + 51.50 * \text{age} - 1.86 * \text{age}^2 + 86.10 * \text{height}$

Age in years; sex = 0 if male and sex = 1 if female; height in meters.

Additional information, including the amount of time walked (to quantify endurance, as all patients may not complete the full 6-minute walk), as well as the use and change of assistive device will also be recorded.

Pulmonary function testing

Secondary efficacy endpoints measured by pulmonary function tests (PFT) will include the assessment of MEP and MIP in the upright position. Additional parameters of respiratory function, including assessment of FVC, MIP, and MEP in the supine position. FEV₁, and PEF in the upright and supine positions will be considered exploratory or tertiary endpoints.

All PFTs will be reported centrally from BMS following pulmonary software specification and user requirement (4).

The percent predicted values for MIP and MEP will be calculated (9, 10). The normal reference values used for % predicted calculation will be dependent on each patient’s age, gender, and weight (Table 6). For each patient, the same equations used for the baseline will be used to calculate the predicted values (eg, if a patient started at ≤17 years of age and turns 18 during the study, he/she will still use the pediatric formula after turning to 18). For analysis purposes, the age will be calculated based on (assessment date - birth date + 1)/365.25. Weight for age <18 will be based on the most recent valid value at or prior to the assessment date. The percent (%) predicted value is defined as (absolute measurement/normal reference value) * 100.

Since the reference values will be available only for patients of age 7 years or older, the % predicted MIP and MEP will not be derived for patients aged <7.

Table 6 - Reference equations for predicted value of MEP and MIP

Test/Age at baseline	Male	Female
MEP		
≥18 years old (9)	$174 - 0.83 * \text{age}$	$131 - 0.86 * \text{age}$
7–17 years old (10)	$35 + 5.5 * \text{age}$	$24 + 4.8 * \text{age}$
MIP		
≥18 years old (9)	$120 - 0.41 * \text{age}$	$108 - 0.61 * \text{age}$
7–17 years old (10)	$44.5 + 0.75 * \text{weight}$	$40 + 0.57 * \text{weight}$

Age in years; weight in kg.

Hand-held dynamometry (lower extremity muscle strength)

Equipment for hand-held dynamometry (11) using the make technique will be standardized across sites. During the treatment period, the assessment will be completed before the IMP infusion. Stabilization procedures for all muscles groups will be followed to avoid use of compensatory muscles. To complete a make test, the examiner holds the dynamometer stationary while the patient exerts a maximal force against the dynamometer. The patient makes a gradual increase in force and then completes an isometric hold for 4-5 seconds.

Lower extremity strength in the muscle groups detailed below will be tested by the same physical therapist or trained assessor.

- Hip Flexion,
- Hip Extension,
- Hip Abduction,
- Hip Adduction,
- Knee Flexion,
- Knee Extension,

- Ankle Dorsiflexion,
- Ankle Plantar Flexion.

The limb tests will be completed bilaterally to account for differences in the generated force for the dominant and non-dominant limb. Every muscle group will be measured two times and the highest value will be reported in the e-CRF. Patients may use noninvasive ventilation during the dynamometry assessment.

Measurements from selected muscle groups will be summed to generate the summary score of the lower extremity muscle strength and lower extremity strength percent predicted. Specifically, no healthy predicted values are available for ankle plantar flexion and hip adduction thus the following 6 muscle groups (both left and right side) are used in calculating the summary score.

- Hip Flexion,
- Hip Extension,
- Hip Abduction,
- Knee Flexion,
- Knee Extension,
- Ankle Dorsiflexion

The reference equations to determine healthy predicted results for each muscle group are provided in [Table 7](#), [Table 8](#) and [Table 9](#). For the patients with age >16 at baseline, the predicted muscle strength will be calculated using the adult reference equations in [Table 7](#). For the patients with baseline age between 3 and 16 years old, the predicted muscle strength will be calculated using the pediatric reference questions in [Table 8](#) and [Table 9](#). For pediatric patients, the same reference equations will be used to calculate the predicted results from both left and right sides within each muscle group. The predicted muscle strength normal reference is only available for patients of 6 years or older for the majority of muscle groups from existing publications.

Table 7 - Adult (age >16) muscle strength reference equations to determine healthy predicted results in Newton (N)

Muscle Group	Test side	Equations*
Hip Flexion (12)	R	$9.8067 [-(age \times .33) + (gender \times 19.19) + ((weight/height^2) \times .66) + 34.44]$
Hip Flexion (12)	L	$9.8067 [-(age \times .29) + (gender \times 18.75) + ((weight/height^2) \times .47) + 36.05]$
Hip Extension (12)	R	$9.8067 [-(age \times .21) + (gender \times 15.19) + ((weight/height^2) \times .14) + 33.52]$
Hip Extension (12)	L	$9.8067 [-(age \times .23) + (gender \times 15.02) + ((weight/height^2) \times .17) + 33.88]$
Hip Abduction (13)	R & L	$195.24 - 62.4(1-gender) - 1.184(age) + .198 (weight \times 9.8067)$
Knee Flexion (12)	R	$9.8067 [-(age \times .16) + (gender \times 8.78) + ((weight/height^2) \times .08) + 22.47]$
Knee Flexion (12)	L	$9.8067 [-(age \times .17) + (gender \times 7.67) + ((weight/height^2) \times .14) + 21.10]$
Knee Extension (12)	R	$9.8067 [-(age \times .38) + (gender \times 18.44) + ((weight/height^2) \times .62) + 34.41]$
Knee Extension (12)	L	$9.8067 [-(age \times .38) + (gender \times 17.68) + ((weight/height^2) \times .62) + 33.61]$
Ankle Dorsiflexion (12)	R	$9.8067 [-(age \times .12) + (gender \times 7.93) + ((weight/height^2) \times .11) + 22.87]$
Ankle Dorsiflexion (12)	L	$9.8067 [-(age \times .13) + (gender \times 8.12) + ((weight/height^2) \times .15) + 21.91]$

* Age in years; gender: male=1, female=0; weight in kgs; height in meters.

Table 8 - Pediatric muscle strength reference values in Newton (N) (14)

Muscle Group	Gender	Age												
		4	5	6	7	8	9	10	11	12	13	14	15	16
Hip flexors	Boy			182	182	225	232	261	245	198	289	337	301	395
	Girl			162	184	175	195	177	264	232	308	281	288	301
Hip abductors	Boy			128	124	131	153	174	151	158	225	306	356	312
	Girl			109	122	117	124	104	140	171	227	244	257	244
Knee extensors	Boy			156	157	185	194	267	239	225	296	370	362	396
	Girl			148	177	166	173	198	265	250	346	280	325	373
Knee flexors	Boy	111	105	158	180	185	195	268	218	201	273	307	327	382
	Girl	92	99	154	171	160	180	175	246	221	301	271	282	336
Foot dorsal flexors	Boy	71	76	104	130	137	141	154	149	170	218	257	267	291
	Girl	75	76	95	114	121	137	130	178	177	214	207	220	232

Table 9 - Pediatric muscle strength reference values in Newton (N) (15)

Muscle Group	Gender	Age Groups					
		3.5-5.5	5.5-7.5	7.5-9.5	9.5-11.5	11.5-13.5	13.5-15
Hip extensors	Boy	80	131	170	210	226	277
	Girl	76	124	157	174	226	267

If a patient is not covered by one of the reference equations, specifically 15-16 years old for hip extension, the reference equation for the oldest age group available (13.5-15 years) will be used.

The summary score of the lower extremity strength will be the sum of the 12 measurements from the 6 muscle groups (left and right measurements from each muscle group). The percent predicted muscle strength will be calculated separately for the 12 measurements from the 6 muscle groups. The percent predicted value of the total score for the lower extremity strength will be the average of the 12 percent predicted values from the 6 muscle groups. If any of the 12 measurements from the 6 muscle groups in lower extremity strength is missing, the summary score of the lower extremity strength is missing. In that case, the percent predicted of the summary score is also missing.

- ***Quick motor function test***
- The QMFT is an observer administered test comprising 16 items specifically difficult for patients with Pompe disease (16). The items are scored separately on a 5-point ordinal scale (ranging from 0 to 4) with a total score of all items ranging between 0 and 64 points with higher score representing better outcome. If any of the 16 items is missing, the total score of the QMFT will be considered as missing.
- ***12-Item short-form health survey***

The SF-12 is comprised of a subset of 12 items from the SF-36 to reproduce the PCS and MCS scales (17). The SF-12 will be administered to assess health-related quality of life in patients 18 years or older at screening/baseline.

More specifically, SF-12 consists of 4 2-item health domain scales, including, physical functioning (PF), role-physical (RP), role-emotional (RE) and mental health (MH), as well as 4 1-item health domain scales, including, bodily pain (BP), general health (GH), vitality (VT) and social functioning (SF). The PCS and MCS scores for a patient are weighted sums of the 12 item scores (18).

When a patient fails to complete all 12 items, a Maximum Data Recovery method is used to first estimate missing item scores and then to predict the PCS and MCS summary scores (18). Specifically, for the 4 2-item health domain scales (PF, RP, RE, MH), a model using the item response theory (IRT) is developed to estimate a missing value on an item based upon a responder's response to an answered item. If neither item is completed, the corresponding scale is missing. For the 4 1-item scales, if the single item is not completed, the corresponding scale is missing. If no data are missing after this estimation step, the PCS and MCS scores can be calculated via the standard weighted sums; otherwise, an established and validated prediction model may be used to estimate the PCS and MCS scores for those responders who have observed or estimated scores on at least 7 out of the 8 health domains. If more than one scale is missing then neither PCS nor MCS can be estimated. Moreover, the PF scale cannot be missing to calculate the PCS score, while the MH scale cannot be missing to calculate the MCS score. For analysis purpose, the scoring of SF-12 will be provided by QualityMetric Inc, based on Scoring Software Version 4.5 of the SF-12v2 Health Surveys.

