2.5.5 Additional efficacy analyses including PRO endpoints

All other exploratory efficacy endpoints will be summarized descriptively and analyzed using a similar method for the primary efficacy endpoint described in [Section 2.5.1](#). For PDSS/PDIS, following the scoring method and algorithm, results will be summarized by descriptive statistics, MMRM, and responder analysis. The analyses will be based on mITT population.

Analyses of efficacy data in extension treatment (ETP)

Unless otherwise specified, ETP efficacy analyses will use the mITT population, where patients will be considered to be in the treatment group to which they were randomized.

All efficacy endpoints will be summarized descriptively at each study visit, as well as the last observation available during the study. For study visits in ETP (beyond week 49), both changes from baseline and changes from ETP baseline (week 49) will be presented.

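### SAP Table 5 fixes the 6MWT reference equation by age at baseline but enters current age, so % predicted distance drifts upward in patients enrolled in mid to late adolescence, most after 18

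*SAP*

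**What the plan says.** SAP 2.1.3.2 (Six-minute walk test) derives % predicted distance from Table 5. The column that selects the equation is headed "Age at baseline": under 18 gives a sex-specific paediatric quadratic in age plus a height term, and 18 or over gives a linear adult equation. The inputs are updated over time. On age, "For analysis purposes, the age at each assessment will be calculated based on (assessment date - birth date + 1)/365.25". The height input is likewise refreshed, using the latest valid measurement on record. Nothing caps age or moves the patient to the adult equation at 18.

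The 6MWT text does not spell out that the paediatric equation is kept after 18; the table heading gives that rule. The next subsection states the same convention openly for MIP and MEP: a patient who starts on the paediatric equation and comes of age on study "he/she will still use the pediatric formula after turning to 18".

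Metres walked is the key secondary endpoint (SAP 2.1.3.2, 2.5.1.1.1, 2.5.2). % predicted distance has a supportive MMRM (SAP 2.5.1.1.2) and enters the correlations with immunogenicity (SAP 2.6.11). For the extension, SAP 2.5.5 says "All efficacy endpoints will be summarized descriptively at each study visit, as well as the last observation available during the study".

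**The concern.** A % predicted value should change only if the patient walks a different distance or if the expected distance for a healthy peer really changes. Here the selector is frozen and the age input keeps moving, so the quadratic is evaluated outside the age band that Table 5 gives it. Past its peak a quadratic falls at an increasing rate. The denominator shrinks and the patient appears to improve.

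Follow-up can run to Week 289 (Protocol 10.1.5.1, 17.3.4), about five and a half years, and all patients receive avalglucosidase alfa in the extension. An upward artefact there would read as a durable gain on the test drug.

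**Working it through.** The plan states no % predicted 6MWT figure, so there is nothing to reproduce first.

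**Inputs from the documents.** With a = age in years and h = height in metres (Table 5):
- boys: 196.72 + 39.81a - 1.36a² + 132.28h
- girls: 188.61 + 51.50a - 1.86a² + 86.10h
- adults: 868.8 - 2.99a, less 74.7 for women

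Week 49 is Day 337 (SAP Table 14): 336/365.25 = 0.92 years after Day 1. Week 289 is 288 weeks later: 2016/365.25 = 5.52 years.

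**Assumptions, not in the documents.** Distance and height are held constant. The range is 300-500 m, height 1.60-1.90 m (male) and 1.50-1.75 m (female). The worked case uses 450 m, 1.75 m and 1.63 m.

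**1. Turning points.** Boys: 39.81/(2 × 1.36) = 14.6 years. Girls: 51.50/(2 × 1.86) = 13.8 years. Both curves fall well before 18.

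**2. Worked case, age 17 at baseline, 450 m.**
- Girl at 17: 188.61 + 875.50 - 537.54 + 140.34 = 666.9 m, so 450/666.9 = 67.5%. At Week 289 (age 22.52) predicted distance is 545.4 m, so 82.5%. Drift +15.0 points.
- Boy at 17: 711.9 m, so 63.2%. At Week 289: 635.0 m, so 70.9%. Drift +7.7 points.

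**3. Range, age 17.5 at baseline.** The lowest drift comes from the shortest walk and tallest patient, the highest from the longest walk and shortest patient.

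| | Predicted distance: baseline, Week 49, Week 289 (m) | Drift at Week 49 | Drift at Week 289 |
|---|---|---|---|
| Male, 300 m, 1.90 m | 728.2, 719.9, 643.8 | +0.48 | +5.4 |
| Male, 500 m, 1.60 m | 688.5, 680.2, 604.1 | +0.89 | +10.2 |
| Female, 300 m, 1.75 m | 670.9, 656.8, 539.2 | +0.96 | +10.9 |
| Female, 500 m, 1.50 m | 649.4, 635.3, 517.7 | +1.71 | +19.6 |

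**4. Where the direction changes.** With no growth, % predicted rises over the 48 weeks to Week 49 only for baseline ages above about 14.2 (male) or 13.4 (female). A boy of 12 walking 400 m falls by 0.43 points. Growth pushes the same way. From age 17.5, cancelling the Week 49 rise would need 8.3/132.28 = 0.063 m of growth in a boy and 14.1/86.10 = 0.164 m in a girl.

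**5. Effect of holding age at 18.0.** Predicted distance stays at 704.2 m (boy) and 653.3 m (girl). At 450 m the 17-year-old girl reaches 68.9% at Week 289, a drift of +1.4. The boy reaches 63.9%, a drift of +0.7.

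**6. Effect of switching to the adult equation at 18.** Predicted distance jumps to 868.8 - 53.82 = 815.0 m (man) and 740.3 m (woman). At 450 m the girl drops from 68.9% to 60.8% and the boy from 63.9% to 55.2% overnight.

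**7. The same cap on MEP (Table 6), at 22.5 years.**
- Girls: current rule 24 + 4.8 × 22.5 = 132.0; capped 110.4; adult equation 111.7.
- Boys: current rule 35 + 5.5 × 22.5 = 158.8; capped 134.0; adult equation 155.3.

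The cap brings girls close to the adult value and moves boys away from it.

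**The case against.** The strongest case against concerns consequence, not arithmetic.

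- **Nothing tested depends on it.** The 6MWT step in the hierarchy uses metres. This stands in full.
- **No paediatric long-term efficacy summary is specified.** A reader might infer that one drifting adolescent would dominate such a summary. The documents do not support that. Extension efficacy is summarised in the mITT population by randomised group (SAP 2.5.5), the under-18 subgroup analysis is confined to the PAP (SAP 2.5.4), the separate paediatric group is for safety (SAP 2.6), and children enrolled directly into open label have their efficacy listed only (SAP 2.2). One patient drifting by 15 points in an arm of about 48 moves the arm mean by 15/48 = 0.3 points.
- **The general extension summary may not include it.** The sentence covering all efficacy endpoints does not name % predicted distance, so its use there is likely but not certain.
- **Follow-up may be shorter.** Week 289 is a maximum. Participation can end at country approval, directly enrolled children stop at Week 241 (Protocol 10.1.7.3.1), and the SAP's analysis windows end at Week 265. At Week 265 the 17-year-old girl's drift is still about +12.9 points (559.9 m, 80.4%).
- **One equation per patient is a deliberate convention.** It is, and the fix keeps it. The convention does not require age to run on without limit.
- **The adult equation is a weak yardstick at 18.** The SAP's reference list describes its source as adults older than 20. That is a further reason not to switch equations. The drift itself does not depend on the adult equation.

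**Conclusion.** The point holds as a small correction to a supportive and descriptive measure. The rule as written gives an upward drift in % predicted distance, at constant metres and height, for patients enrolled in mid to late adolescence. From age 17.5 it is at most about 0.9 points (male) or 1.7 points (female) at Week 49, and about 5-10 or 11-20 points at the Week 289 maximum. These sizes rest on the assumed distances and heights and on no further growth.

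Two other stronger readings should be resisted. A reader might infer that every adolescent's value is inflated, or that extrapolation past 18 is the whole cause. Younger, growing adolescents may show a flat or falling value, and the curves already decline inside the under-18 band. A reader might also infer that the paediatric MEP equation needs the same cap; for boys that would create a larger discrepancy than it removes. Finally, calling the range past 18 an extrapolation rests on Table 5's own limit, because the documents do not give the source study's age range.

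**What to change.** Add one sentence under Table 5: for patients under 18 at baseline, age is held at 18.0 in the paediatric 6MWT equation for every assessment after the 18th birthday. This keeps one equation per patient and avoids the step that a switch to the adult equation would cause. Leave the MEP rule in Table 6 as it is.

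The cost is one sentence and one line of derivation code. There are two small downsides. Predicted distance no longer changes with age after 18 in these few patients. The fall before 18 remains: a girl aged 16 at entry walking 450 m would still move from 66.5% to 68.9%, against 78.1% at Week 289 without the cap.
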